| CYP | cytochrome P450 |
| ECG | electrocardiogram |
| EDC | electronic data capture |
| ETT | Early Termination of Treatment |
| EU | European Union |
| F/F | homozygous for F508del |
| F/G | heterozygous for F508del and a gating mutation |
| F/MF | heterozygous for F508del with a second CFTR allele carrying a minimal function mutation that is not responsive to TEZ, IVA, and TEZ/IVA |
| F/RF | heterozygous for F508del and a residual function mutation |
| F508del | CFTR gene mutation with an in-frame deletion of a phenylalanine codon corresponding to position 508 of the wild-type protein |
| F508del | CFTR protein lacking the phenylalanine normally found at position 508 of the wild-type protein |
| FDA | Food and Drug Administration |
| FDC | fixed-dose combination |
| FEF _{25%-75%} | forced expiratory flow, midexpiratory phase |
| FEV ₁ | forced expiratory volume in 1 second |
| FSH | follicle-stimulating hormone |
| FVC | forced vital capacity |
| GCP | Good Clinical Practice |
| GPS | Global Patient Safety |
| HIPAA | Health Insurance Portability and Accountability Act |
| HR | heart rate |
| IA | interim analysis |
| ICF | informed consent form |
| ICH | International Council for Harmonization |
| IDMC | independent data monitoring committee |
| IEC | independent ethics committee |
| IND | Investigational New Drug (application) (US) |
| IPD | important protocol deviation |
| IRB | institutional review board |

| Abbreviation | Definition |
|---------------------|--|
| IVA | ivacaftor |
| LUM | lumacaftor |
| max | maximum value |
| MedDRA | Medical Dictionary for Regulatory Activities |
| MF | minimal function |
| min | minimum value |
| MMRM | mixed-effects model for repeated measures |
| OATP1B1 | organic anion transporting polypeptide 1B1 |
| OL-FAS | Open-label Full Analysis Set |
| OL-SS | Open-label Safety Set |
| PD | pharmacodynamic, pharmacodynamics |
| P-gp | P-glycoprotein |
| PK | pharmacokinetic, pharmacokinetics |
| ppFEV ₁ | percent predicted forced expiratory volume in 1 second |
| PR | PR interval, segment |
| PT | Preferred Term |
| QRS | the portion of an ECG comprising the Q, R, and S waves, together representing ventricular depolarization |
| QT | QT interval |
| QTc | QT interval corrected |
| QTcF | QT interval corrected by Fridericia's formula |
| RD | respiratory domain |
| RF | residual function |
| RNA | ribonucleic acid |
| RR | interval from the onset of 1 QRS complex to the next |
| SAE | serious adverse event |
| SAP | statistical analysis plan |
| SD | standard deviation |
| SI | SI units (International System of Units) |
| SOC | System Organ Class |
| SUSAR | suspected, unexpected, serious adverse reaction |
| SwCl | sweat chloride |
| TC | triple combination |
| TE | treatment-emergent |
| TEAE | treatment-emergent adverse event |
| TEZ | tezacaftor |
| ULN | upper limit of normal |
| US | United States |

5 INTRODUCTION

5.1 Background

Cystic fibrosis (CF) is an autosomal recessive chronic disease with serious morbidities and frequent premature mortality. CF affects more than 70,000 individuals worldwide¹ (approximately 30,000 in the US² and 45,000 in the EU³). Based on its prevalence, CF qualifies as an orphan disease.^{4,5}

CF is caused by decreased quantity and/or function of the CFTR protein due to mutations in the *CFTR* gene.⁶ CFTR is an ion channel that regulates the flow of chloride and other ions across epithelia in various tissues, including the lungs, pancreas and other gastrointestinal organs, and sweat glands.⁷ Decreased CFTR quantity or function results in the failure to regulate chloride transport in these tissues leading to the multisystem pathology associated with CF.⁸ In the lungs, obstruction of airways with thick mucus, establishment of a chronic bacterial infection in the airways, and damaging inflammatory responses are all thought to play a role in causing irreversible structural changes in the lungs, leading to respiratory failure. Progressive loss of lung function is the leading cause of mortality.⁹

The most common disease-causing *CFTR* mutation is *F508del*, which accounts for approximately 70% of the identified alleles in people with CF.¹⁰ Approximately 40% to 45% of people with CF are homozygous for *F508del* (F/F), and approximately 85% have at least 1 *F508del* allele.^{2,3}

Based on the understanding of the molecular defects caused by *CFTR* mutations, 2 complementary approaches have been developed to address the decreased quantity and/or function of CFTR in order to enhance chloride transport in patients with CF. Correctors facilitate the cellular processing and trafficking to increase the quantity of CFTR at the cell surface. Potentiators increase the channel open probability (channel gating activity) of the CFTR protein delivered to the cell surface to enhance ion transport. With differing mechanisms of action, a combination of correctors and potentiators increases *F508del* CFTR-mediated chloride transport more than either type of modulator alone.

The therapeutic activity of CFTR modulators has been established with products developed by Vertex and approved for the treatment of CF: ivacaftor (IVA) monotherapy (Kalydeco™), lumacaftor (LUM)/IVA (Orkambi®), and tezacaftor (TEZ)/IVA (Symdeko™/Symkevi®).

VX-445 is a next-generation CFTR corrector. In vitro, the triple combination (TC) of VX-445, TEZ, and IVA (VX-445/TEZ/IVA) increased CFTR chloride transport more than any of the dual combinations (VX-445/TEZ, VX-445/IVA, and TEZ/IVA) or individual components (VX-445, TEZ, and IVA) when added to human bronchial epithelial (HBE) cells derived from 2 groups of CF patients: those heterozygous for *F508del* with a second *CFTR* allele carrying a minimal function (MF) mutation that is not responsive to TEZ, IVA, and TEZ/IVA (F/MF genotypes); and those homozygous for *F508del* (F/F genotypes).

Additional information about VX-445/TEZ/IVA can be found in the Investigator's Brochure.

5.2 Study Rationale

This study will provide data on the long-term safety, efficacy, and durability of VX-445/TEZ/IVA in CF subjects who are heterozygous for the *F508del* mutation and a gating (F/G) or residual function (F/RF) mutation.

6 STUDY OBJECTIVES

6.1 Primary Objective

To evaluate the long-term safety and tolerability of VX-445/TEZ/IVA in subjects with CF who are heterozygous for the *F508del* mutation and a gating (F/G) or residual function (F/RF) mutation

6.2 Secondary Objectives

- To evaluate the long-term efficacy of VX-445/TEZ/IVA
- To evaluate the pharmacodynamics (PD) of VX-445/TEZ/IVA

7 STUDY ENDPOINTS

7.1 Primary Endpoint

Safety and tolerability of long-term treatment with VX-445/TEZ/IVA based on adverse events (AEs), clinical laboratory values, ECGs, vital signs, and pulse oximetry.

7.2 Secondary Endpoints

- Absolute change in percent predicted forced expiratory volume in 1 second (ppFEV₁)
- Absolute change in sweat chloride (SwCl)
- Absolute change in body mass index (BMI)
- Absolute change in BMI z-score
- Absolute change in body weight
- Absolute change in CFQ-R respiratory domain (RD) score

7.3 Exploratory Endpoints

- Absolute change in CFQ-R non-RD scores
- Inflammatory mediators
- Blood biomarkers

8 STUDY POPULATION

Eligibility will be reviewed and documented by an appropriately qualified member of the investigator's team before subjects are enrolled.

Subjects who meet all of the inclusion criteria and none of the exclusion criteria will be eligible. In the criteria below, "parent study" refers to Study VX18-445-104 (Study 104).

8.1 Inclusion Criteria

1. Subject (or his or her legally appointed and authorized representative) will sign and date an ICF, and, when appropriate, an assent form.
2. Willing and able to comply with scheduled visits, treatment plan, study restrictions, laboratory tests, contraceptive guidelines, and other study procedures.
3. Did not withdraw consent from the parent study.
4. Meets at least 1 of the following criteria:
 - Completed study drug treatment in the parent study.
 - Had study drug interruption(s) in the parent study, but without prematurely discontinuing study drug in the parent study and completed study visits up to the last scheduled visit of the Treatment Period of the parent study.
5. Willing to remain on a stable CF treatment regimen (as defined in Section 9.5) through completion of study participation.

8.2 Exclusion Criteria

1. History of any illness or any clinical condition that, in the opinion of the investigator, might confound the results of the study or pose an additional risk in administering study drug to the subject.
2. Pregnant and breast-feeding females. All female subjects, regardless of childbearing potential status, must have a negative pregnancy test at the Day 1 Visit before receiving the first dose of study drug.
3. History of drug intolerance in the parent study that would pose an additional risk to the subject in the opinion of the investigator (e.g., subjects with a history of allergy or hypersensitivity to the study drug).
4. Current participation in an investigational drug study (other than the parent study). Participation in a non-interventional study (including observational studies, registry studies, and studies requiring blood collections without administration of study drug) and screening for another Vertex study is permitted.

9 STUDY IMPLEMENTATION

[figure not shown]
9.1 Study Design

This is a Phase 3, multicenter, open-label study for subjects who completed the last Treatment Period visit in the parent study (Study 104) and meet eligibility criteria (see Section 8). A schematic of the study design is shown in [Figure 9-1](#).

All subjects will receive VX-445/TEZ/IVA at the same dosage as that evaluated in Study 104. Study drug administration is described in Section 9.6.

Study visits and assessments to be conducted are shown in [Table 3-1](#). All visits will occur within the windows specified.

Study drug is defined in Section 10.

Figure 9-1 VX18-445-110 Study Design

IVA: ivacaftor; TEZ: tezacaftor

Notes: Parent study refers to Study 104. The timing of the Day 1 Visit, relative to the last scheduled visit of the parent study, is detailed in Section 9.1.1. The figure is not drawn to scale.

9.1.1 Treatment Period

Treatment Period assessments are listed in [Table 3-1](#).

Subjects will receive the first dose of study drug on Day 1 after obtaining informed consent (and assent, when applicable), confirming eligibility, and completing any pre-dose assessments. Subjects who enroll in this study on a study drug interruption will NOT receive the first dose of study drug until they meet the resumption criteria in [Section 9.8](#); before receiving study drug, subjects will repeat all Day 1 assessments.

Study drug administration details are provided in [Section 9.6](#).

The Day 1 Visit of this study should be on the same day as the last scheduled visit of the parent study.

Subjects whose Day 1 Visit is NOT within 1 day of the last scheduled visit in the Treatment Period of the parent study will have all Day 1 assessments performed.

Subjects whose Day 1 Visit is within 1 day of the last scheduled visit in the Treatment Period of the parent study will NOT have to repeat assessments that were performed as part of the last scheduled visit of the parent study Treatment Period.

9.1.2 Safety Follow-up

The Safety Follow-up Visit is scheduled to occur 28 (\pm 7) days after the last dose of study drug. The Safety Follow-up Visit assessments are listed in [Table 3-1](#).

The Safety Follow-up Visit is required for all subjects. However, subjects who transition within 28 days of the last dose of study drug to either a commercially available or managed access program-supplied next-generation corrector TC regimen, or to another qualified Vertex study, will complete the Week 96 Visit (or the Early Termination of Treatment [ETT] Visit, if the transition occurs before the Week 96 Visit). In these cases, the Week 96 Visit (or the ETT Visit) will replace the Safety Follow-up Visit.

For subjects who complete an ETT Visit 3 weeks or later following the last dose of study drug, the ETT Visit will replace the Safety Follow-up Visit ([Section 9.1.3](#)).

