3 SCHEDULE OF ASSESSMENTS

The schedule of assessments is in [Table 3-1](#). All visits will be scheduled relative to the Day 1 Visit in this study.

The Cystic Fibrosis Questionnaire–Revised (CFQ-R) must be completed before any other assessment (except signing of the informed consent form [ICF]) at relevant clinic visits. Remaining assessments may be performed in any order when more than 1 assessment is required at a particular time point. All assessments will be performed before study drug dosing (Section [9.6.1](#)), unless noted otherwise.

Table 3-1 VX18-445-110: Treatment Period and Safety Follow-up Visit

| Event/Assessment ^a | Treatment Period | | | | | | | ETT Visit ^b | Safety Follow-up Visit 28 (± 7) Days After Last Dose ^c | Comments |
|---|--------------------|-------------------|-----------------------------------|---|--------------------|-----------------------------|--------------------|------------------------|---|---|
| | Day 1 ^d | Day 15 (± 3 Days) | Weeks 4, 8, 16, 24, 36 (± 5 Days) | Weeks 12, 20, 28, 32, 40, 44, 52, 56, 64, 68, 76, 80, 88, 92 (± 5 Days) | Week 48 (± 5 Days) | Weeks 60, 72, 84 (± 5 Days) | Week 96 (± 5 Days) | | | |
| Clinic visit | X | X | X | | X | X | X | X | X | |
| Telephone contact | | | | X | | | | | | Assess the subject's status, any AEs, concomitant medications, treatments, and procedures |
| ICF and assent (when applicable) | X | | | | | | | | | Section 8 |
| Inclusion and exclusion criteria confirmation | X | | | | | | | | | Section 8 |
| CFQ-R | X | | Weeks 4, 8, 24 | | X | Week 72 | X | X | X | Must be completed before any other assessments (except signing of ICF) at relevant clinic visits (Section 11.5.3) |
| Weight and height | X | X | X | | X | X | X | X | X | Measured with shoes off. Height will be collected only for subjects ≤21 years of age (Section 11.5.2) |

^a All assessments will be performed before study drug dosing (Section 9.6.1), unless noted otherwise.

^b If the subject prematurely discontinues study drug treatment, an ETT Visit should be scheduled as soon as possible after the decision to discontinue treatment (Section 9.1.3).

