| | Day 1 ^d | Day 15 (± 3 Days) | Weeks 4, 8, 16, 24, 36 (± 5 Days) | Weeks 12, 20, 28, 32, 40, 44, 52, 56, 64, 68, 76, 80, 88, 92 (± 5 Days) | Week 48 (± 5 Days) | Weeks 60, 72, 84 (± 5 Days) | Week 96 (± 5 Days) | | | |
| Study drug dosing | Day 1 through evening before Week 96 Visit | | | | | | | | | Section 9.6.1 |
| Medications review | Continuous from signing of the ICF through completion of study participation | | | | | | | | | Completion of study participation is defined in Section 9.1.5 |
| Treatments and procedures review | | | | | | | | | | |
| AEs and SAEs | Continuous from signing of the ICF through completion of study participation | | | | | | | | | Sections 13.1.1.3 and 13.1.2.2 |

AE: adverse event; CFQ-R: Cystic Fibrosis Questionnaire-Revised; ETT: Early Termination of Treatment; FSH: follicle-stimulating hormone; ICF: informed consent form; OE: ophthalmologic examination; SAE: serious adverse event; SwCl: sweat chloride; TC: triple combination

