9.1.5 Completion of Study Participation

Completion of study participation for each individual subject is defined as: the Safety Follow-up Visit; or, in situations in which the ETT Visit or the Week 96 Visit replace the Safety Follow-up Visit (Section 9.1.2), the ETT Visit or the Week 96 Visit.

If subjects withdraw consent or assent, completion of study participation is defined as date of withdrawal of consent or assent, whichever is earlier (Section 9.9).

If subjects are lost to follow-up (Section 9.1.4), the date of completion of study participation will be defined as the date of last contact.

The end of study is defined in Section 13.2.8.

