12.3 Statistical Analysis

12.3.1 General Considerations

Continuous variables will be summarized using the following descriptive summary statistics: the number of subjects (n), mean, SD, median, minimum value (min), and maximum value (max). The precision of the measurement for each continuous variable will be specified in the SAP. Unless otherwise specified, min and max values will be reported with the same precision as

the units of the raw data. The mean, median, and SD will be reported to 1 additional decimal place. Any values that require a transformation to standard units (metric or SI) will be converted with the appropriate precision.

Categorical variables will be summarized using counts and percentages. Percentages will be presented to 1 decimal place.

The baseline value, unless otherwise specified, for the long-term safety analysis will be the most recent non-missing measurement (scheduled or unscheduled) collected before the first dose of VX-445/TEZ/IVA either in the parent study or the open-label study, as applicable. The baseline value for the long-term efficacy analysis will be defined as the most recent non-missing measurement (scheduled or unscheduled) collected before the first dose of study drug in the parent study. For assessments collected in duplicate or triplicate, the baseline will be defined as the average of non-missing values.

Baseline characteristics of subjects in the open-label study will be the same as the baseline characteristics in the parent study.

Change (absolute change) from baseline will be calculated as post-baseline value - baseline value.

The **Efficacy Analysis Period** in the open-label study will include the time from the first dose of study drug in the open-label study to the last scheduled efficacy visit in the open-label study, unless otherwise specified.

The **Treatment-emergent (TE) Period** in the open-label study will include the time from the first dose of study drug in the open-label study to 28 days after the last dose of the study drug in the open-label study or to the completion date of study participation (as defined in Section 9.1.5), whichever occurs first.

The long-term efficacy analysis will be performed by parent study for the Efficacy Analysis Period in the open-label study.

In general, long-term safety analyses will be performed in a pooled fashion.

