12.3.4.1 Adverse Events

For analysis purposes, AEs will be classified as pretreatment AEs, TEAEs, or post-treatment AEs, defined as follows:

- **Pretreatment AE:** any AE that occurred before the first dose of VX-445/TEZ/IVA in the TE Period in the open-label study
- **TEAE:** any AE that worsened (either in severity or seriousness) or newly developed at or after the first dose date of VX-445/TEZ/IVA in the TE Period in the open-label study
- **Post-treatment AE:** any AE that worsened (either in severity or seriousness) or newly developed after the TE Period in the open-label study

For AEs with missing or partial start dates, if there is no clear evidence that the AEs started before or after study drug treatment, then the AEs will be classified as TEAEs.

AE summary tables will be presented for TEAEs only and will include the following:

- All TEAEs
- TEAEs by strongest relationship
- TEAEs by maximum severity
- TEAEs leading to treatment discontinuation
- TEAEs leading to treatment interruption
- Serious TEAEs
- TEAEs leading to death
- Grade 3 and Grade 4 TEAEs
- Frequently reported TEAEs

Summaries will be presented by MedDRA SOC and PT using frequency counts and percentages (i.e., number and percentage of subjects with an event). When summarizing the number and percentage of subjects with an event, subjects with multiple occurrences of the same AE or a continuing AE will be counted once. Only the maximum severity level will be presented in the severity summaries, and the strongest relationship level will be presented in the relationship summaries. An AE overview table will be provided. In addition, a listing containing individual subject level AE data for all deaths and other serious and significant AEs will be provided separately. All AEs, including pre- and post-treatment AEs, will be presented in individual subject data listings.

Exposure-adjusted event rates may also be provided.

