13.1.1.3 Documentation of Adverse Events

All AEs will be collected from the time the ICF is signed until the subject completes study participation, as defined in Section [9.1.5](#).

All subjects will be queried, using nonleading questions, about the occurrence of AEs at each study visit. When possible, a constellation of signs and/or symptoms will be identified as 1 overall event or diagnosis. All AEs for enrolled subjects will be recorded in the CRF and source document. AEs for subjects who are screened but not subsequently enrolled will be

recorded only in the subject's source documents. The following data will be documented for each AE:

- Description of the event
- Classification of “serious” or “nonserious”
- Date of first occurrence and date of resolution (if applicable)
- Severity
- Causal relationship to study drug(s)
- Action taken
- Outcome
- Concomitant medication or other treatment given

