8.2 Open Label Extension Period

OL Efficacy Period for Part A: The time from the first dose of study drug in the OLS to the last efficacy assessment, which may be collected up to the Week 96 Visit or the earlier of Day 673 and the end of study participation if subject does not have the Week 96 Visit. This analysis period will be used with the OL-FAS for Part A to analyze the efficacy data during the OLS.

OL Safety Period for Part A: The time from the first dose of study drug in the OLS to 28 days after the last dose date of the study drug in the OLS or to the completion date of study participation (defined in CSP Section 9.1.5) in Part A, whichever occurs first. This analysis period will be used with the OL-SS for Part A to analyze the safety data during the OLS.

The **Treatment-emergent (TE) Period for Part A** is same as the OL Safety Period for Part A.

Note: for subjects who depart study 110 to participate in another qualified Vertex study and return in study 110, the above defined analysis period will exclude the time between the last dose before the discontinuation from study 110 and the first dose after re-enter in study 110.

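### Subjects who start commercial or managed-access TC after an off-drug gap leave AE collection and the TE Period at the Week 96 (or ETT) Visit, up to 27 days early by the text

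*Protocol*

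**What the plan says.** - **Replacement rule (Protocol 9.1.2).** The Safety Follow-up Visit is required of everyone, but for "subjects who transition within 28 days of the last dose of study drug to either a commercially available or managed access program-supplied" TC the Week 96 Visit, or the ETT Visit if the switch comes earlier, takes its place. The same rule covers subjects who enter another of the sponsor's studies.
- **Completion date (Protocol 9.1.5).** Participation normally ends at the Safety Follow-up Visit. Where that visit is replaced, the section names the replacing visit instead: "the Week 96 Visit replace the Safety Follow-up Visit (Section 9.1.2), the ETT Visit or the Week 96 Visit".
- **AE collection (Protocol 13.1.1.3).** "All AEs will be collected from the time the ICF is signed until the subject completes study participation". All-cause SAE reporting stops at the same point (13.1.2.2); after that only related SAEs are reported.
- **TE Period.** Protocol 12.3.1 runs it "to 28 days after the last dose of the study drug in the open-label study or to the completion date of study participation", whichever comes first. SAP 8.2 has the same rule for Part A: "28 days after the last dose date of the study drug in the OLS or to the completion date of study participation".
- **Reporting (Protocol 12.3.4.1).** "AE summary tables will be presented for TEAEs only and will include the following". AEs after the TE Period go to listings.
- **A narrower rule (Protocol 9.9).** A subject taken off study drug to start commercial TC is excused the Safety Follow-up Visit if commercial dosing follows on at once.

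**The concern.** The natural reason for dropping off-drug follow-up is that the subject is no longer off drug. That reason applies from the first dose of the new regimen. Section 9.1.2 applies it from the Week 96 or ETT Visit, whatever the wait in between. A subject who waits two or three weeks for supply is off the modulator, still inside the plan's own 28-day post-dose window, and already treated as having completed.

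Long-term safety is the primary endpoint, so which AEs are collected and counted as treatment-emergent matters. Delays are foreseeable: 9.9 itself mentions subjects who cannot yet get the commercial product because of reimbursement or insurance.

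Only new non-serious AEs and unrelated SAEs are exposed. Related SAEs (13.1.2.2), pregnancies up to 90 days after the last dose (11.6.7.2) and AEs still open at the visit (13.1.1.7) stay covered. Subjects who switch without a gap, who do not switch, or who roll over to Part B and stay on study drug are unaffected.

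**Working it through.** The plan gives no figure for this gap, so the check is day arithmetic on its rules. Count the last dose as day 0.

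**1. Inputs**
- Table 3-1, study drug dosing: "Day 1 through evening before Week 96 Visit". The Week 96 Visit is therefore day 1.
- Table 3-1, follow-up column: "Safety Follow-up Visit 28 (± 7) Days After Last Dose". The window is 28 − 7 = day 21 to 28 + 7 = day 35.
- TE Period end = min(28, completion day), from Protocol 12.3.1 and SAP 8.2.

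**2. Without replacement.** If the Safety Follow-up Visit is on day 21, the TE Period ends on day 21. If it is on day 28 or later, the TE Period ends on day 28.

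**3. Week 96 route with replacement.** Completion is day 1, so the TE Period ends on min(28, 1) = day 1. If the new regimen starts on day *t* (at most 28), the off-drug days after the visit are *t* − 1:

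| Start day *t* | Unobserved days |
|---|---|
| 1 | 0 |
| 8 | 7 |
| 15 | 14 |
| 21 | 20 |
| 28 | 27 |

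The limit by the text is 28 − 1 = 27 days. It is 21 − 1 = 20 days if a waiting subject has a Safety Follow-up Visit on the first permitted day and that visit is taken as completion.

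**4. Managed-access switch after early termination.** With the ETT Visit on day *e*, the gap is *t* − *e*, at most 28 − *e*: 27, 21, 14 and 8 days for *e* = 1, 7, 14 and 20. From 3 weeks on, the ETT Visit replaces follow-up for everyone (9.1.3), so that case is separate.

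**5. Commercial switch after early termination.** Under 9.1.2, a start within 28 days means the ETT Visit replaces the Safety Follow-up Visit. Under 9.9, the visit is excused only when commercial dosing follows at once, so by implication it stays due after a gap. The two sections give different answers.

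**6. Same event, two classifications.** Take a new non-serious AE on day 10 after Week 96. If TC starts on day 28 with no Safety Follow-up Visit held first, completion is day 1 and the AE is outside the TE Period. If TC starts on day 29, the visit is due and the same AE is a TEAE. On day 10 the site may not know which will apply.

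**7. Pooled size.** The documents do not give the number of gap switchers. As an assumption, take 2% to 20% of 250 subjects (5 to 50), with 7 to 20 days each:
- low: 5 × 7 = 35 days
- high: 50 × 20 = 1,000 days
- extreme, 27 days for all 50: 50 × 27 = 1,350 days

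Planned treatment time is 250 × 96 × 7 = 168,000 days. The shares are 35/168,000 = 0.02%, 1,000/168,000 = 0.6% and 1,350/168,000 = 0.8%.

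**The case against.** **The TE cut-off is deliberate and nothing is really lost.** Both documents state explicitly that the earlier date governs. Until a waiting subject switches, the Safety Follow-up Visit is still due, so a site may well keep recording AEs. All AEs are listed, and SAP 9.4.1 adds SAE and death listings with a TEAE flag. This stands in part: a recorded event is not lost. But it is then a post-treatment AE, absent from every summary table, and once the subject switches the protocol no longer asks for it.

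**The size is unknown.** This stands. No document gives a typical time to switch or a count of gap switchers, and the count could be zero. The 20-day figure follows from the visit window and does not describe what subjects do.

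**The governing text may have changed.** The supplied protocol is a single-part, 96-week study, while the SAP describes two parts and cites the most recent approved protocol. The current Part A exit rules are not visible, and rollover to Part B may shrink the affected group. This stands as a limit: the finding is about the supplied text. SAP 8.2 still ends the Part A TE Period by reference to Protocol 9.1.5.

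**Moving the completion date has side effects.** It would also extend the CYP3A inducer and inhibitor restrictions (9.4.1), and the stable-regimen rule, the bar on new long-term medication and medication recording (9.5). This stands, and the fix deals with it.

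**Stronger readings to avoid.** A reader might infer that all switchers lose safety follow-up, or that every early terminator moving to commercial TC does. The documents do not support either: without a gap there are no off-drug days to lose, and 9.9 can be read as keeping the visit for a commercial switcher who has a gap.

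**Conclusion.** The point holds as a minor design weakness. Under the supplied protocol, a subject who starts commercial or managed-access TC within 28 days of the last dose, but after a gap, leaves AE collection and the TE Period at the Week 96 Visit, or at the ETT Visit for managed-access switchers. On the Week 96 route this removes up to 27 off-drug days by the text, or up to 20 if follow-up is held on day 21. For commercial switchers after early termination it is a conflict between 9.1.2 and 9.9.

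A reader might infer that the safety results are biased. The documents do not support that. Safety analysis is descriptive and pooled (Protocol 12.3.4), so no planned comparison is affected. Under the assumed shares the affected time is at most 0.8% of planned treatment days, even in the extreme case. That share measures time, not events, and rests on an assumed number of gap switchers.

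**What to change.** 1. **Gap switchers only** (new regimen started more than 1 day after the Week 96 or ETT Visit): continue AE and SAE collection and the TE Period to the earlier of the first dose of the new regimen and 28 days after the last study dose, but not to a date before that visit. Add one telephone contact that records AEs and the start date of the new regimen, which the plan does not otherwise collect after completion. State in Protocol 9.1.5 and 12.3.1 and in SAP 8.2 that the medication restrictions in 9.4.1 and 9.5 still end at the Week 96 or ETT Visit. If that is not wanted, name their short extension as a downside; it would run to day 28 at most, the nominal day of the Safety Follow-up Visit.
2. **Align 9.1.2 with 9.9**, so that early terminators moving to commercial TC are excused follow-up only when they switch at once.
3. **Carry the same wording** into the Part A exit rules of the current two-part protocol.

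No change is proposed for subjects who switch without a gap or who enter another of the sponsor's studies.

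Cost: wording in the protocol and SAP, and one call per gap switcher, of a kind already in Table 3-1. The laboratory, ECG and vital-sign data of the Safety Follow-up Visit are not recovered, and a 1-day gap stays unobserved.
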